8.6 Contingency for Violation of Proportional Odds Assumption

The proportionality assumption underlying the proportional odds model will be assessed by examining plots of empirical cumulative logits across treatment groups and comparing observed versus model-predicted probabilities. If there is substantial evidence of an unacceptable degree of model misspecification (e.g. the empirical cumulative logits from different treatment groups are clearly crossing) then a nonparametric instead of parametric win ratio analysis will be presented. To implement a Bayesian nonparametric version of the win ratio analysis, cell probabilities underlying the win ratio calculation (Table 3) will be estimated empirically by assigning noninformative independent Dirichlet distributions to the set of category probabilities within each treatment group. Other details of the calculations are essentially identical to those described for the primary analysis. The prior for this nonparametric Bayesian analysis was chosen for simplicity and computational convenience and may be revised in a subsequent version of the Statistical Analysis Plan.

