8 ANALYSIS OF THE PRIMARY ENDPOINT

8.1 Parametric Win Ratio Analysis

The primary endpoint analysis will focus on assessing the overall effects of standard of care plus HCQ versus no HCQ (Hypothesis #1) and AZM versus no AZM (Hypothesis #2), as detailed in Section 3.1. Analysis will be performed in the intention-to-treat (ITT) population, as defined in Section 3.1. The analytic approach will be a model-based parametric implementation of the win ratio framework. [1] In a conventional win ratio analysis, the win ratio statistic is calculated by forming all possible pairs of 1 participant from the treatment group and 1 participant from the control group and then dividing the proportion of pairs for which the treated patient has a better outcome by the proportion of pairs for which the untreated patient has a better outcome. The PROTECT trial analysis will estimate this same underlying win ratio quantity but will do so parametrically using a statistical model. The parametric approach was chosen because it facilitates analysis in a Bayesian statistical framework using a range of Bayesian prior distributions. A Bayesian nonparametric implementation of the win ratio with a non-informative prior distribution was tested in simulations prior to trial launch and was found to be anti-conservative in the sense that the prior distribution assigned high prior probability to the hypothesis of large or small win ratio and this led to high probability of a spurious signal during interim analyses. The underlying quantities to be estimated in this analysis are as follows:

Win Ratio for Hypothesis #1 (HCQ versus no HCQ): The win ratio for HCQ versus no HCQ is defined as the probability that a randomly selected patient who was randomized to HCQ has a better outcome than a randomly selected patient from the same AZM subgroup who was randomized to no HCQ divided by the probability that a randomly selected patient who was randomized to HCQ has a worse outcome than a randomly selected patient from the same AZM subgroup who was randomized to no HCQ.

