8.4 Estimation Methods

Model parameters will be estimated in a Bayesian statistical framework using Markov Chain Monte Carlo sampling for inference [2]. Advantages of the Bayesian framework include the ability to express analysis results in terms of clinically relevant probabilities and the ability to perform exact inference on complicated functions of model parameters, for example, the win ratio.

Prior distribution

Bayesian analysis requires the specification of a probability distribution representing prior information about the set of unknown model parameters before observing the study data. Because no single choice of prior can accurately capture the viewpoints of all potential stakeholders, the analysis will be performed with multiple choices for the prior distribution. For the primary analysis, the prior for treatment main and interaction effects will be a set of independent normal distributions:

$$\begin{aligned}\mu &\sim N(\text{mean} = 0, \text{SD} = 0.3537) \quad (\text{main effect}) \\ \gamma_1 &\sim N(\text{mean} = 0, \text{SD} = 0.3537) \quad (\text{main effect}) \\ \gamma_2 &\sim N(\text{mean} = 0, \text{SD} = 0.3537) \quad (\text{main effect}) \\ \delta_1 &\sim N(\text{mean} = 0, \text{SD} = 0.2651) \quad (\text{interaction}) \\ \delta_2 &\sim N(\text{mean} = 0, \text{SD} = 0.2651) \quad (\text{interaction})\end{aligned}$$

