The main effects SD = 0.3537 was chosen to imply that odds ratios for HCQ versus no HCQ and AZM versus no AZM are between 0.5 and 2.0 with 95% probability assuming that the interaction effects are zero. The interaction SD = 0.2651 was chosen to imply that the ratio of odds ratios for HCQ versus no HCQ across two levels of AZM and the ratio of odds ratios for AZM versus no AZM across two levels of HCQ would each be between 0.8 and 1.25 with 80% probability. The intercept parameters θ_k will be assigned central t distributions with 3 degrees of freedom and SD = 10 subject to the constraint $\theta_0 < \theta_2 < \dots < \theta_7$, which is the default prior in the R package 'brms'. To explore sensitivity to the choice of prior, the analysis will be repeated using two alternative forms for the prior distribution. The first alternative prior distribution will be the same as above but will set $\delta_1 = \delta_2 = 0$ with 100% probability. The second alternative prior will assign a non-informative improper uniform distribution to the set of main effects and interaction terms. Additional prior distributions may be implemented post-hoc for manuscript presentations or by request of external reviewers and stakeholders.

Computation

Posterior means and credible intervals for the Win Ratio quantities of interest will be calculated using Hamiltonian Markov Chain Monte Carlo (MCMC) simulations as implemented in the R package 'brms'. [4,4] To reduce Monte Carlo error, we will generate a large number of simulated parameter values and will perform graphical and other diagnostic checks to ensure convergence. To perform inference on Win-Ratio^{HCQ} and Win-Ratio^{AZM} we note that each of these quantities is a function of the cell probabilities $\boldsymbol{\pi}$ defined in Table 3 which in turn are functions of the model parameters $\Theta = (\theta_0, \theta_1, \theta_2, \theta_3, \theta_4, \theta_7, \theta_6, \theta_7, \mu, \gamma_1, \gamma_2, \delta_1, \delta_2)$. We use notation Win-Ratio^{HCQ}(Θ) and Win-Ratio^{AZM}(Θ) to denote the value of the win ratios as a function of unknown model parameters. Posterior mean point estimates of the win ratios will be calculated as

$$\begin{aligned}\widehat{\text{Win-Ratio}}^{\text{HCQ}} &= \frac{1}{M} \sum_{i=1}^M \text{Win-Ratio}^{\text{HCQ}}(\Theta^{(i)}) \\ \widehat{\text{Win-Ratio}}^{\text{AZM}} &= \frac{1}{M} \sum_{i=1}^M \text{Win-Ratio}^{\text{AZM}}(\Theta^{(i)})\end{aligned}$$

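### The Section 8.6 fallback is of the kind Section 8.1 reports as anti-conservative, and Section 11 does not clearly keep it out of the interim signals (minor)

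*SAP*

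**What the plan says.** Section 8.1 explains why a parametric model was chosen. "A Bayesian nonparametric implementation of the win ratio with a non-informative prior distribution was tested in simulations prior to trial launch", and it was judged anti-conservative because its prior put much weight on large and small win ratios; "this led to high probability of a spurious signal during interim analyses".

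Section 8.4 acknowledges that no one prior suits every reader, so "the analysis will be performed with multiple choices for the prior distribution". The primary prior is skeptical: normal, centred at no effect, SD 0.3537 for main effects and 0.2651 for interactions. A non-informative prior appears there only as a sensitivity analysis: "The second alternative prior will assign a non-informative improper uniform distribution to the set of main effects and interaction terms".

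Section 8.6 covers failure of proportional odds. If there is substantial evidence of unacceptable misspecification, for example if "the empirical cumulative logits from different treatment groups are clearly crossing", "then a nonparametric instead of parametric win ratio analysis will be presented". The cell probabilities are then estimated "by assigning noninformative independent Dirichlet distributions to the set of category probabilities within each treatment group". The concentration is not given. The prior is described as a choice of convenience that "may be revised in a subsequent version of the Statistical Analysis Plan".

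Section 11 first equates the interim methods with those of Section 8. It then says that the WHO-scale framework is the parametric win ratio from the proportional odds model. Section 11.1 gives a 14% probability of a false efficacy signal, rests the control of wrong conclusions on a suitably skeptical prior, and sets no threshold for the final analysis.

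**The concern.** The plan turns a type of method down for a stated fault and then names the same type as its replacement, without referring to the fault. Two things follow.

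- **Interim looks.** Section 8.6 is part of Section 8. A reporting statistician could read Section 11 as admitting the fallback, and would have to settle the matter while seeing results by treatment group. Curves cross by chance most often when data are few, which is also when the prior counts most and when Section 8.1 warns of spurious signals.
- **Final analysis.** The noninformative prior would be the only one stated, in place of the parametric result. The reader would lose the skeptical prior on which Section 11.1 relies instead of a multiplicity adjustment.

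**Working it through.** **Inputs from the SAP:** prior SDs 0.3537 and 0.2651 (8.4); first efficacy look at 75 participants (11); efficacy signal if P(win ratio ≥1.25) >80% or P(win ratio >1) >95%, and inefficacy or harm signal if P(win ratio <1) >80% or P(win ratio <0.9) >75% (Table 5); 14% over 500 patients (11.1).

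**Assumed, because the SAP does not give them:** WHO scores 0 to 8 at A 5/25/25/10/12/5/5/3/10%, B 2/15/20/15/18/8/8/4/10% or C 10/40/20/8/8/3/3/2/6% (C for the prior only); 20% AZM-ineligible; Dirichlet concentration 1 or 0.5; 18 looks, from 75 to 500 in steps of 25. Only the HCQ comparison was simulated.

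**1. The plan's 14%.** The log odds ratio without interaction was simulated with information per patient (1 − Σp³)/12, the N(0, 0.3537) prior and a look after every patient, for three assumed score distributions. The false efficacy signal was 12.3-13.2%, within 2 points of 14%. The stated figure is therefore consistent with the parametric model; none is given for the fallback.

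**2. Why the prior matters early.** Prior precision is 1/0.3537² = 7.99. For distribution A, Σp³ = 0.0354, so information per patient is 0.9646/12 = 0.0804. This gives 6.0 at N=75 and 40.2 at N=500. The prior's share is 7.99/(7.99 + 6.03) = 57% at the first look and 7.99/(7.99 + 40.2) = 17% at the end.

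**3. Implied priors (200,000 draws).**

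| Quantity | Primary prior | Dirichlet 1 | Dirichlet 0.5 |
|---|---|---|---|
| One pair (2 vs 1): P(win ratio ≥1.25) | 20-22% | 36% | 40% |
| One pair: P(outside 0.5-2) | 1.0-1.4% | 27% | 45% |
| HCQ win ratio, ratio of sums: P(≥1.25) | 22-23% | 27% | 33% |
| HCQ win ratio, printed 8.2 average: P(≥1.25) | 22-24% | 39% | 50% |

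The mechanism described in 8.1 is confirmed. For the three-stratum quantity that Table 5 monitors, however, the gap is modest unless the printed average of ratios is used. That average alone moves P(win ratio >1) under the Dirichlet prior from the symmetric 50% to 62% (concentration 1) or 65% (0.5).

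**4. How often a switch might occur.** The rule assumed here is that the pooled HCQ and no-HCQ cumulative curves differ by more than 5 points in both directions. With proportional odds exactly true and no effect, this happens in 35-37% of trials at N=75, 17-19% at N=150 and 2% at N=500.

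**5. Signals over 18 looks, compared within trial** (1,200 null trials under A, 700 under B, 700 with real crossing).

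- *No effect, fallback only after crossing.* Efficacy signal, printed formula: 12.6-14.5% against 12.1-13.5%, an excess of 0.4-1.0 point (SE 0.2-0.3). Ratio of sums: excess 0.0-0.2 point. Inefficacy or harm: −0.4 to −0.1 point (printed), +0.1 to +0.7 (ratio of sums).
- *Real 8-point crossing, true win ratio 1.* Efficacy excess 1.6-4.1 points (printed; SE 0.5-0.8), −0.6 to +1.0 (ratio of sums). Inefficacy or harm: −0.9 (printed), +2.9 to +3.0 (ratio of sums). The last shift is the same for both concentrations, so it comes from the change of model and not from the prior.
- *No effect, fallback at every look, which 8.6 does not provide for.* Efficacy signal in one set of runs: 20-27% against 12-13.5% (printed), 13-18% against 11-12% (ratio of sums). A separate set of 600 null trials gave 17-24% (printed) and 11-17% (ratio of sums).

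**6. At N=500.** The 95% credible interval is 2-8% wider on the log scale. P(win ratio >1) moves by a median of 0.02-0.04 (90th percentile 0.06-0.10).

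**The case against.** The strongest reply is that Section 11 already answers the interim question. Its sentence on the WHO scale names the parametric model, and a specific statement normally governs a general one. Section 8.6 uses the language of reporting, asks for substantial evidence of misspecification and flags its prior as provisional. Table 5 is only a set of proposed guidelines.

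Much of this stands. The text does lean towards exclusion, and the crossing rule used in the check is looser than substantial evidence would suggest, so the switching frequencies are illustrative. What does not go away is that nothing says which sentence governs once 8.6 is triggered, that an optional revision leaves the current text in force, and that 8.6 is silent on the finding in 8.1.

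A reader might infer more than the SAP supports:

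- *That the interim monitoring will use a method known to inflate signals.* Section 11 does not say so and points the other way.
- *That the false-signal rate rises from 14% to 20% or more.* That requires the fallback at every look, and a good part of the rise belongs to the averaging formula in 8.2.
- *That error at the final analysis is inflated.* The fault reported in 8.1 concerns interim signals, and 11.1 sets no final threshold, so there is no such error rate.
- *That 8.6 restores the very method that was tested.* Section 8.1 does not name the prior it tried, so only the kind of method can be matched.

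**Conclusion.** The inconsistency between 8.1 and 8.6 is real and rests on the SAP's own wording; the openness of Section 11 is real but slight. The expected effect is small: 0 to 1 point on false efficacy signals if the fallback follows crossing under the null, and little movement at N=500. These sizes depend on the assumed score distributions, Dirichlet concentration, look schedule and crossing rule, on a normal approximation to the proportional-odds posterior, and on the HCQ comparison alone. At the final analysis the loss is one of presentation: no skeptical result is required beside the fallback. Severity: minor.

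**What to change.** 1. State in 8.6 and 11 that at interim looks the Table 5 thresholds apply only to the proportional-odds posterior, and that any Dirichlet result goes to the DSMB as a sensitivity analysis. The drawback is that a possibly misspecified model still drives the signals; the sensitivity display mitigates this. Cost: wording.
2. If 8.6 is triggered at the final analysis, always report the proportional-odds result with its skeptical prior beside the nonparametric one, and repeat the caveat from 8.1. Cost: wording and one extra table row.
3. If the sponsor wants a skeptical fallback prior, calibrate it on the HCQ and AZM win ratios that the trial reports, for example with a partial proportional-odds model that keeps the shared-effect priors of 8.4. A single pair is the wrong target. A Dirichlet with a common centre that matches the primary prior for one pair needs about 45-55 pseudo-patients per group (6 × 45 = 270 to 6 × 55 = 330 in all). It then gives P(HCQ win ratio ≥1.25) of only 8-10% (ratio of sums) or 10-13% (printed formula), against 22-24% under the primary prior. Cost: a simulation run and modest programming.

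Stating the Dirichlet concentration and what counts as clear crossing would be a useful addition.

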8.7 Exploratory Pairwise Group Comparisons

The treatment effects estimated by the primary analysis are averages in the sense that the comparison of HCQ versus no HCQ is aggregated over AZM subgroups and the comparison of AZM versus no AZM is aggregated over HCQ subgroups. The primary reason for targeting average as opposed to subgroup-specific treatment effects which are potentially more informative for practice is the expected lack of statistical precision for estimating subgroup-specific effects. In order to shed light on potential treatment effect heterogeneity across AZM and HCQ subgroups, we will report estimated odds ratios and accompanying 95% credible intervals comparing treatment groups on a pairwise basis from the primary analysis proportional odds model.

9 ANALYSIS OF SECONDARY EFFICACY ENDPOINTS

The major treatment group comparisons of HCQ versus no HCQ and AZM versus no AZM will be repeated using the following secondary clinical endpoints in place of the primary endpoint:

- Mortality during the index hospitalization
- Number of days on mechanical ventilation during the index hospitalization
- Progression to mechanical ventilation during index hospitalization.
- Day 28 WHO ordinal scale
- Days from randomization until hospital discharge
- Duration of fever after randomization
- Duration of supplemental oxygen use after randomization

Analysis of **index hospitalization mortality status** and **mechanical ventilation** will be performed using logistic regression. The analysis will use the same predictors as the primary endpoint proportional odds model and will use the same Bayesian prior distribution for the main effects and interaction effects parameters. For the ventilation endpoint, patients on ventilator at baseline will be excluded. To facilitate interpretation, parameter estimates from the logistic regression model will be re-expressed as win ratios, risk ratios, and/or risk differences.

Analysis of the **day 28 WHO scale** will be identical to the primary endpoint analysis using the day 28 assessment in place of the 14 day assessment.

Analysis of **length of hospital stay, duration of fever, and duration of supplemental oxygen use** will be based on a continuation ratio model for discrete time-to-event data treating death as a competing risk. For length of stay, the continuation ratio approach models that probability of being discharged on day $d + 1$ conditional on being alive and in-hospital on day d and assumes that covariates have a multiplicative effect on this probability. For patients who die prior to discharge, the patient's discharge date will be set to the last date of the patient's potential follow-up time. The interpretation is similar for duration of fever and supplemental oxygen. Predictor variables in the continuation ratio model will be identical to the primary endpoint proportional odds model and will use a similar prior distribution for the main effects and interaction terms.

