3.2 Secondary Objectives

The trial will also evaluate the HCQ and AZM hypotheses using the following secondary endpoints:

- Mortality during the index hospitalization
- Number of days on mechanical ventilation during the index hospitalization
- Progression to mechanical ventilation during index hospitalization
- World Health Organization ordinal scale on day 28
- Days from randomization until hospital discharge
- Duration of fever after randomization
- Duration of supplemental oxygen use after randomization

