7.1 Missing Data

Every effort will be made to obtain complete data. In the case where missing data remain, the following procedures will be followed. These procedures are based on the assumption that missing data will be rare and may be revised if that assumption is violated.

- **Primary endpoint.** If a day 14 WHO scale assessment is unavailable then analysis will be based on the closest assessment within 21 days of randomization with ties broken by taking the earlier assessment. If a patient is known to have died or been re-hospitalized but the exact date is unknown then data entry may be based on an estimated value. If no estimate of a patient's status is available within 21 days of randomization then the primary endpoint will be regarded as missing and will not be imputed. The approach to handling missing primary endpoint data may be revised if >5% of patients have no assessments within a window of 14 ± 3 days or >2% of patients have no assessments within a window of 14 ± 6 days.
- **Mortality during the index hospitalization.** Missing in-hospital mortality status will not be imputed.
- **Number of days on mechanical ventilation during index hospitalization.** No imputation will be performed for this endpoint.
- **Progression to mechanical ventilation during index hospitalization.** No imputation will be performed for this endpoint.
- **Day 28 WHO scale.** If unavailable then analysis will use the closest measurement from days 14 to 40 with ties broken by taking the later assessment. Data entry may be based on estimated dates if exact dates for a status assessment is unavailable.
- **Days from randomization until hospital discharge.** No imputation will be performed for this endpoint.
- **Duration of fever after randomization.** No imputation will be performed for this endpoint.
- **Duration of supplemental oxygen use after randomization.** No imputation will be performed for this endpoint.

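### Section 9 gives no rule for death in the two ventilation endpoints, so an arm with more deaths could look better on them

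*SAP*

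**What the plan says.** SAP Sections 3.2 and 9 list two ventilation endpoints among the secondary endpoints: "Number of days on mechanical ventilation during the index hospitalization" and "Progression to mechanical ventilation during index hospitalization". Neither name includes death.

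On method, Section 9 states: "Analysis of index hospitalization mortality status and mechanical ventilation will be performed using logistic regression". The next rule on population is "For the ventilation endpoint, patients on ventilator at baseline will be excluded". Estimates from the logistic model may then be re-expressed as win ratios, risk ratios or risk differences. Section 9 names no model suited to the day count: a logistic model does not fit a count, and the day count is not among the continuation-ratio endpoints.

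Section 7.1 says of each of the two endpoints: "No imputation will be performed for this endpoint".

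By contrast, the Section 9 analysis of length of stay, fever and oxygen use "will be based on a continuation ratio model for discrete time-to-event data treating death as a competing risk". For length of stay, a patient who dies before discharge is given a discharge date at the end of potential follow-up, and the interpretation for fever and oxygen is said to be similar. On the WHO scale in Section 6.1, death is the worst category (8), below ventilation (6 and 7).

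**The concern.** Death and ventilation compete. A patient who dies first can no longer be intubated, and a patient who dies on the ventilator stops accruing ventilator days. If an endpoint has no rule for death, the dead patient falls by default on the favourable side.

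The SAP recognises this for three duration endpoints and for the WHO scale, but not for these two, and gives no reason for the difference. The route is plausible in this trial: Section 10 lists ventricular arrhythmia, torsade de pointes and QT prolongation as events of special interest, and such an event, if fatal, could come before any intubation.

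What is at stake is how two secondary results are read. Section 7 frames results as probability statements without adjustment for multiple comparisons, and Section 11.1 leaves it to stakeholders to act on them without a fixed threshold. A favourable posterior probability for progression that arose from deaths would go to them as it stands.

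**Working it through.** The SAP gives no event rate, sample size or power figure for either ventilation endpoint, so there is no plan figure to reproduce. The check traces how the written rules score particular patients, then uses assumed rates to show direction and size.

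**Step 1. Scoring under the written rules**

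| Patient, not ventilated at baseline | Progression | Ventilator days | WHO scale after the event |
|---|---|---|---|
| Recovers, never intubated | No | 0 | Below 6 |
| Dies, never intubated | No | 0 | 8 |
| Intubated, dies on ventilator day 2 | Yes | 2 | 8 |
| Intubated, extubated on day 10, survives | Yes | 10 | Below 6 once extubated |

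The 0 entries assume that the day count covers all patients, which the SAP does not specify. The second patient is observed, not missing, so the no-imputation rule in Section 7.1 does not change the entry. On progression, the second patient ties with the first and beats the fourth. On days, the third patient beats the fourth.

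**Step 2. Progression, with assumed rates**

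Control: 15% intubated, 5% die without intubation. The drug only moves 3 points from the first group to the second.

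- Progression: 15% versus 15 − 3 = 12%.
- Odds ratio = (0.12/0.88) / (0.15/0.85) = 0.77.
- As a binary win ratio: (0.88 × 0.15) / (0.12 × 0.85) = 0.132/0.102 = 1.29 in favour of the drug.
- Ventilation or death: 15 + 5 = 20% versus 12 + 8 = 20%.
- Death without intubation: 5% versus 8%.

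A 5-point shift gives 15% versus 10%, odds ratio (0.10/0.90) / (0.15/0.85) = 0.63, again with 20% in both arms on the composite.

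A second assumed setting has 20% intubated and 3% dying without intubation in the control arm. Shifts of 2, 5 and 8 points give progression of 18%, 15% and 12%, with odds ratios of 0.88, 0.71 and 0.55. The composite stays at 23% in both arms.

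**Step 3. Ventilator days, with assumed values**

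Among ventilated patients, survivors have 12 days and those who die have 4. Let f be the proportion who die.

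- Mean days = 12(1 − f) + 4f. At f = 25% this is 10; at f = 50% it is 8.
- Averaged over all patients with 15% ventilated in both arms: 0.15 × 10 = 1.5 versus 0.15 × 8 = 1.2 days.
- Ventilator-free days to day 28, with death scored 0, among ventilated patients: (28 − 12)(1 − f), which is 12 versus 8.

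Starting from f = 30% and rising to 40%, 50% or 60%, mean days fall from 9.6 to 8.8, 8.0 or 7.2, and ventilator-free days fall from 11.2 to 9.6, 8.0 or 6.4. The raw count moves in the favourable direction as deaths rise; the measure that ranks death worst moves in the unfavourable one.

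**The case against.** The strongest reply has four parts.

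- **The coding is inferred.** No sentence in the SAP says that a death without intubation counts as no progression, and a protocol could define the event more fully. This is fair as to wording: a reader might infer that the plan declares death a good result, and it does not. But a logistic model with a single stated exclusion leaves the un-intubated death as an observed non-event unless something else is written. The no-imputation rule concerns missing values and settles nothing either way.
- **The day count has no analysis to criticise.** This stands in part. That half of the point rests on the raw-count definition alone. A comparison of means is an illustration, not a method that the SAP specifies, and the 10 versus 8 days apply to ventilated patients only.
- **The effect need not occur.** A reader might infer that any drug that hastens death would look protective on both endpoints. The documents do not support that. Progression falls only if death pre-empts intubation; deaths after intubation leave it unchanged, and a drug that worsens respiratory failure can raise both measures. The one-for-one shift in the illustration is an assumption.
- **Deaths are visible elsewhere.** In-hospital mortality is a separate secondary endpoint, and death is the worst category on the day 14 and day 28 WHO scales. This limits the damage, but it does not correct either ventilation estimate.

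**Conclusion.** The point holds as a gap in Section 9. Neither ventilation endpoint has a rule for death, while the neighbouring duration endpoints do. As written, an arm with more deaths could look better on progression or on ventilator days. Expressed as a win ratio, progression would also rank a death without intubation above an intubated survivor, against the order of the SAP's own WHO scale.

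Under the assumed rates, the false benefit on progression runs from an odds ratio of 0.88 to 0.55, with 0.77 for a 3-point shift, while ventilation or death does not differ. These figures show direction and plausible size; they are not forecasts.

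A reader might also infer that the primary result or the stopping guidance is at risk. It is not: the primary endpoint ranks death worst, and interim efficacy review under Section 11 and Table 5 uses only the WHO scale and in-hospital death. The consequence is a possibly misleading secondary estimate, which is worth correcting before analysis.

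**What to change.** 1. **Progression.** In patients not ventilated at baseline, analyse mechanical ventilation or death during the index hospitalization with the Bayesian logistic model already in Section 9. Report ventilation alone and death alone beside it. The components are needed because the composite removes the false benefit but, in the illustration, does not itself show the extra deaths.
2. **Ventilator days.** Name a model and state the population. An ordinal analysis with death ranked worst would serve, for example ventilator-free days to day 28 with a stated convention for time after discharge. Show the raw count descriptively.

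The cost is small for progression: both outcomes are already listed and the model exists. Ventilator days need more work, because the 9-category model would have to be set up for a longer scale and the post-discharge convention must be written. The composite mixes two events of different weight. Both changes must be aligned with the protocol's endpoint list, so this may go beyond SAP wording.
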